2.1. Screen Failure (Section 4.5)

Changed From:

All individuals who sign the ICD and withdraw their consent for participation in the study or fail to meet at least one of the eligibility criteria during the initial evaluation will be considered a "screen failure" and their data will not be considered in the final report (except for screen failed subjects with an AE, in which case the demography, subject disposition, and AE information will be entered in the Electronic Data Capture (EDC) system and the AEs will be included in the final report).

Changed To:

All individuals who sign the ICD and withdraw their consent for participation in the study or fail to meet at least one of the eligibility criteria during the initial evaluation will be considered a "screen failure" and their data will be entered in the Electronic Data Capture (EDC) system and the AEs will be included in the final report.

2.2. Additional application details for all IPs (Section 6.5.2)

Changed From:

Different Adhesive Bandages Protocol Number: CCSTOH001689

Version & Date: Amendment 3: Final Version 4.0, 28 Aug 2019

Changed To:

2.3. Study Procedures and Evaluation Schedule (Section 7.2, Table 2)

Changed From:

^cAssessment will be completed remotely approximately 2-4 hours after BLT cream application once numbness is gone.

Changed To:

^cAssessment will be completed remotely approximately 3-4 hours after BLT cream application once numbness is gone.

2.4. Self-Assessment Questionnaire (Section 7.2.5.3)

Changed From:

2-4 hours

Changed To:

3-4 hours

2.5. Visit 17-18 (Day 15-16) (Section 7.2.7)

Changed From:

 Subjects will be reminded of the study instructions. Wound sites will remain uncovered for the remainder of the study.

Changed To:

- At Visit 17: The designated IP will be applied to each test site per the randomization schedule.
- At Visit 18: Subjects will be reminded of the study instructions. Wound sites will remain uncovered for the remainder of the study.

Changed From:

Visits 3-19

Changed To:

Visits 3-20

Different Adhesive Bandages Protocol Number: CCSTOH001689

Version & Date: Amendment 3: Final Version 4.0, 28 Aug 2019

2.7. Serious Adverse Event (SAE) Definition 2 (Section 10.3.2.2)

Added:

 A malfunction that the device (or similar device marketed by the same manufacturer or importer) would be likely to cause death or similar injury if the malfunction were to recur.

Deleted:

- Congenital anomaly/birth defect
- 2.8. Subject Self-Assessment Questionnaire (Day 0 through Day 4) (Appendix VI)

Changed Form:

<Additional Day 0 Instructions: Please complete this questionnaire as soon as the numbness is gone (this will be around 2-4 hours after the numbing cream was applied).>

. . .

4) is the pain (described in #4) brief (**B**), periodic (**P**), or constant (**C**)?

Changed To:

<Additional Day 0 Instructions: Please complete this questionnaire as soon as the numbness is gone (this will be around 3-4 hours after the numbing cream was applied).>

...

4) Is the pain (described in #3) brief (**B**), periodic (**P**), or constant (**C**)?

Different Adhesive Bandages Protocol Number: CCSTOH001689

Version & Date: Amendment 3: Final Version 4.0, 28 Aug 2019

Appendix IX. Summary of Changes – Amendment 2

CLINICAL PROTOCOL CCSTOH001689 AMENDMENT 2

A 28-Day, Single-Center, Randomized, Comparator-Controlled, Proof-of-Principle Study to Assess Wound Healing Efficacies of Different Adhesive Bandages

SUMMARY OF CHANGES

Study Product Name:	N/A
Protocol Number:	CCSTOH001689
IND/IDE/Eudra CT:	N/A
Phase:	N/A
Sponsor:	Johnson & Johnson Consumer, Inc.
	Amendment 2: Final Version 3.0, 20 Aug 2019
Version and Date	Amendment 1: Final Version 2.0, 12 Aug 2019
	Original: Final Version 1.0, 10 Jul 2019

1. REASONS FOR THE AMENDMENT TO THE FINAL PROTOCOL

Sections of protocol CCSTOH001689, "A 28-Day, Single Center, Randomized, Comparator-Controlled, Proof-of-Principle Study to Assess Wound Healing Efficacies of Different Adhesive Bandages", dated August 12, 2019 (Final Version 2.0),

2. PROTOCOL SECTIONS REVISED

The protocol sections that were revised are detailed below. The format is as follows:

- The "Deleted" section represents the original text in Protocol # CCSTOH001689, Final Version 2.0, dated August 12, 2019, that was deleted for Final Version 3.0, dated August 20, 2019.
- The "Changed From" section represents original text in Protocol # CCSTOH001689, Final Version 2.0, dated August 12, 2019, that was changed to new text in Final Version 3.0, dated August 20, 2019. The revised text is indicated in the "Changed To" section.
- The "Added" section represents new text in Protocol # CCSTOH001689, Final Version 3.0, dated August 20, 2019.

2.1. Synopsis (Dose and Mode of Application)

Added:

**Wound sites will remain uncovered once completely healed.

2.2. Synopsis (Measurement and/or Evaluation Schedule)

Changed From:

The following evaluations will be conducted for each wound site at the indicated time points:

- Clinical Grading of Wound Healing Parameters (erythema, edema, epithelial confluence, crusting/scabbing, smoothness, and general wound appearance) – Day 0 through Day 16*
- Scarring Assessment Day 0 and Day 28
- •
- TEWL Measurements Day 0 through Day 14*
- Self-Assessment Questionnaire Day 0 through Day 4

Different Adhesive Bandages Protocol Number: CCSTOH001689

Version & Date: Amendment 3: Final Version 4.0, 28 Aug 2019

Changed To:

The following evaluations will be conducted for each wound site at the indicated time points:

- Clinical Grading of Wound Healing Parameters (erythema, edema, epithelial confluence, crusting/scabbing, smoothness, and general wound appearance) – Day 0 through Day 16* (or until completely healed, if earlier)
- Scarring Assessment Day 0 and Day 28
- •
- TEWL Measurements Day 0 through Day 14*
- Self-Assessment Questionnaire Day 0 through Day 4

2.3. Study Design (Section 3.0)

Changed From:

Between Baseline and Day 16, each wound site will be subjected to one of eight randomly-assigned treatments (see section 6). Treatments include an adhesive bandage that is considered the marketed adhesive bandage benchmark control, a non-marketed adhesive bandage benchmark control, four non-marketed adhesive bandages, and no treatment (uncovered, negative control).

Changed To:

and TEWL (until Day 14). In addition, subjects will assess the wound sites via questionnaire from Day 0 to Day 4,

Between Baseline and Day 16, each wound site will be subjected to one of eight randomly-assigned treatments (see section 6) until day of complete healing. Treatments include an adhesive bandage that is

version & Date. Amendment 3. Final version 4.0, 28 Aug 2019
considered the , a marketed adhesive bandage benchmark control, a non-marketed adhesive bandage
benchmark control, four non-marketed adhesive bandages, and no treatment (uncovered, negative
control).
Once a wound site has completely healed, bandage changes will be discontinued and the
wound will be left uncovered.
0.4 ID= (046 0.50)
2.4. IPs (Section 6.5.2)
Changed From:

All IP application and removal will be performed at the study site as described below by trained study sta
wearing gloves and according to the randomization schedule (see section 6.6).
Each IP unit is for single use; used bandages will not be re-applied and should be discarded by
the Site as described in section 6.3.
the site as described in section 0.5.
Changed To:
All IP application and removal will be performed at the study site as described below by trained study sta wearing gloves and according to the randomization schedule (see section 6.6).
wearing groves and according to the randomization schedule (see section 6.6).
Each IP un
is for single use; used bandages will not be re-applied and should be discarded by the Site as described i
section 6.3.

[figure not shown]
Different Adhesive Bandages Protocol Number: CCSTOH001689

Version & Date: Amendment 3: Final Version 4.0, 28 Aug 2019

...

Added:

Version & Date: Amendment 3: Final Version 4.0, 28 Aug 2019

2.5. Study Procedures and Evaluation Schedule (Section 7.2)

Note: formatting change made in Table 2 to add footnotes to "Clinical grading of wound healing parameters" and "IP application" rows.

Changed From:

DHealed test sites only.

Changed To:

2.6. Identification of Test Sites and Application of Temporary (Semi-Permanent) Dot-Tattoos and Test Site Labels (Section 7.2.3.3)

Changed From:

Eight test sites (i.e. wound sites) will be identified on the volar forearms, four on each forearm, as shown in Figure 5.

Figure 5. Wound Site Placement

Changed To:

Eight test sites (i.e. wound sites) will be identified on the volar forearms, four on each forearm, as shown in Figure 6.

Figure 6. Wound Site Placement

^D At time of complete healing for a particular wound site.

^EClinical grading of wound healing parameters will be performed for a particular test site only until time of complete healing.

^FCompletely healed wound sites will be left uncovered for the remainder of the study

Version & Date: Amendment 3: Final Version 4.0, 28 Aug 2019

2.7. Visits 3-16 (Day 1-14) (Section 7.2.6)

Changed From:

- After the acclimation period, the following evaluations will be conducted for each test site:
 - o Clinical Grading of Wound Healing Parameters, as described in section 7.2.3.5.
 - o Instrumental measurements, as described in section 7.2.3.7.
- The designated IP will be applied to each test site per the randomization schedule.

Changed To:

- After the acclimation period, the following evaluations will be conducted for each test site:
 - o Clinical Grading of Wound Healing Parameters, as described in section 7.2.3.5.
 - o Instrumental measurements, as described in section 7.2.3.7.
- The designated IP will be applied to each test site per the randomization schedule.ⁱⁱ

2.8. Visit 17-18 (Day 15-16) (Section 7.2.7)

Changed From:

- After the acclimation period, the following evaluations will be conducted for each test site:
 - Clinical Grading of Wound Healing Parameters, as described in section 7.2.3.5.
- At Visit 17: The designated IP will be applied to each test site per the randomization schedule.

Changed To:

- After the acclimation period, the following evaluations will be conducted for each test site:
 - Clinical Grading of Wound Healing Parameters, as described in section 7.2.3.5.
 - •
- At Visit 17: The designated IP will be applied to each test site per the randomization schedule.

ⁱ Clinical grading of wound healing parameters will be performed for a particular test site only until time of complete healing

ii Completely healed wound sites will be left uncovered for the remainder of the study.

¹ Clinical grading of wound healing parameters will be performed for a particular test site only until time of complete healing

ii Completely healed wound sites will be left uncovered for the remainder of the study.

Protocol Title: A 28-Day, Single-Center, Randomized, Comparator-Controlled, Proof-of-Principle Study to Assess Wound Healing Efficacies of Different Adhesive Bandages
Protocol Number: CCSTOH001689
Version & Date: Amendment 3: Final Version 4.0, 28 Aug 2019
2.9.

Different Adhesive Bandages Protocol Number: CCSTOH001689

Version & Date: Amendment 3: Final Version 4.0, 28 Aug 2019

Appendix X. Summary of Changes – Amendment 3

CLINICAL PROTOCOL CCSTOH001689 AMENDMENT 3

A 28-Day, Single-Center, Randomized, Comparator-Controlled, Proof-of-Principle Study to Assess Wound Healing Efficacies of Different Adhesive Bandages

SUMMARY OF CHANGES

Study Product Name:	N/A
Protocol Number:	CCSTOH001689
IND/IDE/Eudra CT:	N/A
Phase:	N/A
Sponsor:	Johnson & Johnson Consumer, Inc.
	Amendment 3: Final Version 4.0, 28 Aug 2019
Version and Date	Amendment 2: Final Version 3.0, 20 Aug 2019
version and Date	Amendment 1: Final Version 2.0, 12 Aug 2019
	Original: Final Version 1.0, 10 Jul 2019

1. REASONS FOR THE AMENDMENT TO THE FINAL PROTOCOL

Sections of protocol CCSTOH001689, "A 28-Day, Single Center, Randomized, Comparator-Controlled, Proof-of-Principle Study to Assess Wound Healing Efficacies of Different Adhesive Bandages", dated August 20, 2019 (Final Version 3.0), have been revised to continue the clinical grading of wound healing parameters until Day 16 for all wound sites.

2. PROTOCOL SECTIONS REVISED

The protocol sections that were revised are detailed below. The format is as follows:

 The "Changed From" section represents original text in Protocol # CCSTOH001689, Final Version 3.0, dated August 20, 2019, that was changed to new text in Final Version 4.0, dated August 28, 2019. The revised text is indicated in the "Changed To" section.

2.1. Synopsis (Measurement and/or Evaluation Schedule)

Changed From:

 Clinical Grading of Wound Healing Parameters (erythema, edema, epithelial confluence, crusting/scabbing, smoothness, and general wound appearance) – Day 0 through Day 16* (or until completely healed, if earlier)

Changed To:

[figure not shown]
 Clinical Grading of Wound Healing Parameters (erythema, edema, epithelial confluence, crusting/scabbing, smoothness, and general wound appearance) – Day 0 through Day 16*

2.2. Study Design (Section 3.0)

Changed From:

Each wound site will be photographed (at all time points) and assessed at pre-specified intervals by clinical
grading of wound healing parameters (until Day 16 or completely healed, if earlier),
and TEWL (until Day 14). In addition, subjects will assess the wound sites via questionnaire from
Day 0 to Day 4, and

Changed To:

Different Adhesive Bandages Protocol Number: CCSTOH001689

Version & Date: Amendment 3: Final Version 4.0, 28 Aug 2019

2.3. Study Procedures and Evaluation Schedule (Section 7.2)

Note: formatting change were made in Table 2 to remove the footnote from the "Clinical grading of wound healing parameters" row and to change the footnote on the "IP application" row from F to E.

Changed From:

^EClinical grading of wound healing parameters will be performed for a particular test site only until time of complete healing.

^FCompletely healed wound sites will be left uncovered for the remainder of the study

Changed To:

^ECompletely healed wound sites will be left uncovered for the remainder of the study.

2.4. Visits 3-16 (Day 1-14) (Section 7.2.6)

Changed From:

0

0

- After the acclimation period, the following evaluations will be conducted for each test site:
 - Clinical Grading of Wound Healing Parameters, as described in section 7.2.3.5.
 - o Instrumental measurements, as described in section 7.2.3.7.

The designated IP will be applied to each test site per the randomization schedule.

Changed To:

- After the acclimation period, the following evaluations will be conducted for each test site:
 - o Clinical Grading of Wound Healing Parameters, as described in section 7.2.3.5.
 - o Instrumental measurements, as described in section 7.2.3.7.

The designated IP will be applied to each test site per the randomization schedule.ⁱ

2.5. Visit 17-18 (Day 15-16) (Section 7.2.7)

Changed From:

- After the acclimation period, the following evaluations will be conducted for each test site:
 - Clinical Grading of Wound Healing Parameters, as described in section 7.2.3.5.
 - •

¹ Clinical grading of wound healing parameters will be performed for a particular test site only until time of complete healing ¹¹ Completely healed wound sites will be left uncovered for the remainder of the study.

¹ Completely healed wound sites will be left uncovered for the remainder of the study.

Different Adhesive Bandages Protocol Number: CCSTOH001689

Version & Date: Amendment 3: Final Version 4.0, 28 Aug 2019

• At Visit 17: The designated IP will be applied to each test site per the randomization schedule."

Changed To:

- After the acclimation period, the following evaluations will be conducted for each test site:
 - Clinical Grading of Wound Healing Parameters, as described in section 7.2.3.5.

At Visit 17: The designated IP will be applied to each test site per the randomization schedule.

¹ Clinical grading of wound healing parameters will be performed for a particular test site only until time of complete healing

ii Completely healed wound sites will be left uncovered for the remainder of the study.

ii Completely healed wound sites will be left uncovered for the remainder of the study.

1 INTRODUCTION

The primary goal in wound care is to protect the wound from further damage and to facilitate healing by providing the optimal environment that limits infection, inflammation and scarring. Appropriate wound dressings play an important role in providing this necessary protection and may promote restoration of skin barrier function compared to untreated wounds.

Wound healing is a complex process wherein the skin surface and the underlying tissue must go through an intricate process of tissue repair. The dermis of an uncovered wound is relatively more fibroplastic, fibrotic, and scarred compared to occluded wounds, and is likely to be more inflamed and necrotic in early stages of repair. Exudate, the moisture secretion from the wound site, facilitates the healing process, by providing a variety of bioactive mediators such as enzymes, growth factors and hormones. Wound exudate may also aid in limiting inflammation by providing various immune cells with an ideal medium to destroy invading pathogens such as bacteria, foreign bodies and necrotic tissues. However, exudate in an uncovered wound can lead to scab formation, with trapped inflammatory cells, wound debris, and a layer of desiccated dermal tissue. Covering a wound with an occlusive dressing reduces scab formation and may radically alter the pattern of epidermal wound healing.

Another factor that plays an important role in wound healing is the moisture in the wound environment. As early as 1962, Winter et al., provided the first evidence that keeping wounds moist helps them heal faster compared to dry wounds.

As occlusion affects both the epidermis by enhancing epithelial cell migration and the dermis by enhancing dermal collagen synthesis, maintaining a moist environment may promote the restoration of epidermal barrier function and overall wound healing while making dressing changes relatively easier. Moreover, it has been suggested that the scar left by an occlusively dressed wound is more cosmetically acceptable than that left by an uncovered wound.

1.1 Study Objectives

The objective of this study is to assess the wound healing efficacy (time to complete healing) of different adhesive bandages.

1.2 Study Design

This is a single center, randomized, comparator-controlled, proof-of-principle clinical trial. The target population is 25- to 55-year-old males and females of Fitzpatrick skin types II-III who have uniform skin color on both volar forearms. A sufficient number of subjects will be screened and enrolled to ensure completion of at least 30 subjects.

At Screening (Visit 1; 3 to 7 days prior to Baseline), subjects will be provided with an auxiliary cleanser to use on their forearms and for all body cleansing in place of their regular body cleanser for the duration of the study.

At Baseline (Visit 2, Day 0), a Sciton Er:YAG 2940 laser will be used to induce eight partial-thickness (i.e. minor) wounds on the subjects' forearms (four per arm). The wounds created by this method heal by the migration of epidermal cells from the dermal appendages located in the wound's base (dermal islands) and/or wound borders, and mimic minor wounds similar to real life scraped skin, typically healing in at less than 14 days if left untreated, based on the Site's previous experience.

Each wound site will be [REDACTED] and assessed at pre-specified intervals by clinical grading of wound healing parameters (until Day 16), [REDACTED] [REDACTED] and Trans-Epidermal Water Loss (TEWL) (until Day 14). In addition, subjects will assess the wound sites via questionnaire from Day 0 to Day 4, [REDACTED]

Between Baseline and Day 16, each wound site will be subjected to one of eight randomly-assigned treatments (see section 6). Treatments include an adhesive bandage that is considered the [REDACTED] a marketed adhesive bandage benchmark control, a non-marketed adhesive bandage benchmark control, four non-marketed adhesive bandages, and no treatment (uncovered, negative control). [REDACTED]

All wound sites will be uncovered from Day 16 to Day 28, at which point subjects will return for a scar assessment of each wound site, [REDACTED]

2 INTERIM ANALYSES

No interim analysis is planned for this trial.

3 ANALYSIS SETS

3.1 Primary Analyses Set

The analyses will be based on the Intent-to-Treat (ITT) principle, i.e., all subjects who received laser-induced wounds and started the study treatments will be included in the analysis.

3.2 Per-Protocol Set

Not applicable.

3.3 Safety Analysis Set

The safety analysis will be based on all subjects who have IP applied at least once.

4 EFFICACY ASSESSMENTS AND ENDPOINTS

4.1 Efficacy Assessments

4.1.1 Clinical Grading of Wound Healing Parameters

- Erythema
 - 0 = none/absent
 - 1 = mild
 - 2 = moderate
 - 3 = marked
 - 4 = severe
- Edema
 - 0 = none/absent
 - 1 = mild
 - 2 = moderate
 - 3 = marked
 - 4 = severe
- Epithelial Confluence
 - 0 = none, no epithelial coverage
 - 1 = slight (up to 30%)

Protocol CCSTOH001689
Statistical Analysis Plan

- 2 = moderate (31-60%)
- 3 = extensive (61-90%)
- 4 = almost complete or complete (91-100%), covered with a full layer of new epithelial growth
- Crusting/Scabbing
 - 0 = none
 - 1 = slight (up to 30%)
 - 2 = moderate (31%-60%)
 - 3 = extensive (61%- 90%)
 - 4 = almost complete or complete (91%-100%)
- Smoothness
 - 0 = rough, uneven wound
 - 1 = mild smoothness
 - 2 = moderate smoothness
 - 3 = extensive smoothness
 - 4 = complete smooth, even wound
- General Wound Appearance
 - 0 = Poor
 - 1 = Fair
 - 2 = Good
 - 3 = Very good
 - 4 = Excellent

Half-point grading will be allowed.

4.1.2 Scarring Assessment

- Color
 - 1 = Perfect
 - 2 = Slight mismatch with surrounding skin
 - 3 = Obvious mismatch with surrounding skin
 - 4 = Gross mismatch with surrounding skin
- Finish (matte versus shiny)
 - 1 = Matte
 - 2 = Shiny

Protocol CCSTOH001689
Statistical Analysis Plan

- Contour
 - 1 = Flush with surrounding skin
 - 2 = Slightly proud/indented
 - 3 = Hypertrophic
 - 4 = Keloid
- Distortion
 - 1 = None
 - 2 = Mild
 - 3 = Moderate
 - 4 = Severe
- Texture
 - 1 = Normal
 - 2 = Just palpable
 - 3 = Firm
 - 4 = Hard

[REDACTED] [REDACTED]

[REDACTED]

[REDACTED] [REDACTED]

[REDACTED]

4.1.5 TEWL Measurements

TEWL measurements will be performed for each wound site on Day 0 through Day 14*. The duplicate values of TEWL at each assessment time point will be averaged as the final response value.

[REDACTED] [REDACTED]

[REDACTED]

4.1.7 Self-Assessment Questionnaire

Self-Assessment Questionnaire will be conducted for each wound site on Day 0 through Day 4.

[REDACTED]

4.2 Efficacy Endpoints

4.2.1 Primary Efficacy Endpoint

The primary endpoint of the study will be “Time to Complete Healing”. “Time to Complete Healing” is defined as the time (in days) elapsed from the time of wound creation to 12 PM of the day on which the composite healing score (calculated from the clinical grading of wound healing parameters, as defined below) first meets the complete healing criterion of being at least a score of 8. If a composite healing score does not meet the complete healing criterion by Day 16, the time to complete healing will be censored at the last day on which the composite healing score is available.

The composite healing score will be calculated from the clinical grading of wound healing parameters as follows:

Composite Healing Score = [general wound appearance score + smoothness score + epithelial confluence score] – [erythema score + edema score + crusting/scabbing score]

The composite healing score on a 25-point scale (-12 thru +12) is indicative of the extent of wound healing and will be calculated for each wound site at each evaluation day.

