7. INVESTIGATIONAL PLAN

7.1. STUDY DURATION

The study will consist of 20 visits over approximately 5 weeks with visits scheduled at Screening (Visit 1, 3 to 7 days prior to Visit 2), Day 0 (Visit 2, Baseline/Pre-Wound and Post-Wound time points), daily on Days 1 through Day 16 (Visit 3 through Visit 18), Day 21 (Visit 19), and Day 28 (Visit 20). A subject's Day 0 through Day 28 study visits should be scheduled at approximately the same time of day for each visit (i.e., morning, afternoon, or evening).

Version & Date: Amendment 3: Final Version 4.0, 28 Aug 2019

STUDY PROCEDURES AND EVALUATION SCHEDULE 7.2.

The table below presents a summary of the study procedures and evaluation schedule.

Table 2. Schedule of Events

	:	1	2 -	2	(-	,	7, 9, 11,	8, 10,	,	ļ	,	,	(
Procedures:	Visit:	Screening	Baseline (Pre-Wound)	(Post- Wound)	3 & 4	5	9	13, & 15	12, & 14	16	17	18	19	20
	Day:	-7 to -3	0	0	1 & 2	3	4	5, 7, 9, 11 & 13	6, 8, 10 & 12	14	15	16	21	28
ICD with HIPAA disclosure & Photo Release	4)	×												
Demographics, medical history, and conmeds collection	spe	×												
Review of eligibility/enrollment		×												
Dispense auxiliary cleanser & study instructions	tions	×												
Interview for compliance and changes in			*	X	X	X	X	×	×	×	X	X	×	×
health/AEs/conmeds			·	(AEs only)	<	`	`	,	·	`	<	<	~	<
Randomization			×											
			×	×	×	×	×	×	×	×	×	×	×	
Test site label application			×	×	×	×	×	×	×	×	×	×	X	×
IP Removal					AX	×	X^B	×	XB	χ_{B}	X	X		
5-min acclimation			×	×	ЯX	×	X^B	×	X _B	XB	X	X		×
Clinical grading of wound healing parameters	ers		×	×	X_B	×	X^B	×	XB	XB	×	×		
Scarring assessment			×											×
			×	×	A^B	×	X^B	×	XB	χ_{B}	X	X	X	×
			×	×	A^B	×	X^B	×	XB	XB				
TEWL measurements			×	×	яΧ	×	XB	×	X _B	XB				
			×					X_D	(×
BLT cream application (30 min prior to wounding)	ding)		×											
Test site cleaning and wounding			×											
IP application ^E				×	X _B	×	X^B	X	XB	χ_{B}	X			
Subject self-assessment questionnaire				Xc	×	×	×							
Collect auxiliary product														×
										1	1	1	1	Ī

^cAssessment will be completed remotely approximately 3-4 hours after BLT cream application once numbness is gone.

 $^{^{\}text{D}}\text{At}$ time of complete healing for a particular wound site. $^{\text{E}}\text{Completely}$ healed wound sites will be left uncovered for the remainder of the study.

Version & Date: Amendment 3: Final Version 4.0, 28 Aug 2019

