6.3 Statistical Methods

Summary statistics will be provided at each time point for the primary and secondary efficacy.

Time to complete healing will be analyzed using a survival analysis method. The survival function (cumulative percentage of wounds healed at each time point) will be estimated by the Kaplan-Meier method for each treatment separately. The median time to complete healing will be derived from the estimated survival functions and be compared using the bootstrap re-sampling method.

The pairwise comparison of median complete healing times is performed by the following steps:

- 1) Independently take $B=200$ bootstrap samples with subject as the sampling unit. Each bootstrap sample has the same size as the original sample size and is obtained by sampling subjects with replacement with the original time to complete healing data, say $\{(t_1^b, \dots, t_8^b), b = 1, \dots, B\}$.
- 2) Within each bootstrap sample, estimate the median survival time using KM method for each treatment separately, say $\{\hat{m}_i^b : i = 1, 2, \dots, 8, b = 1, \dots, B\}$.
- 3) Calculate the pairwise difference in median times to complete healing $\hat{\tau}^b = \hat{m}_{i1}^b - \hat{m}_{i2}^b, b = 1, \dots, B$.

Protocol CCSTOH001689
Statistical Analysis Plan

4) Estimate the variance of the median time difference by

$$v(\hat{\tau}) = \frac{1}{B-1} \sum_{b=1}^B (\hat{\tau}^b - \bar{\hat{\tau}})^2$$

$$\text{where } \bar{\hat{\tau}} = \sum_{b=1}^B \hat{\tau}^b / B$$

The null hypothesis of $H_0: M_{i1} = M_{i2}$ can be tested by the following test statistics

$$z = \frac{\hat{M}_{i1} - \hat{M}_{i2}}{\sqrt{v(\hat{\tau})}}$$

Under the null hypothesis, this test statistics asymptotically follows the standard normal distribution. Hence the 2-sided p-value and the 95% confidence interval can be calculated by

$$p = 2 \times \{1 - \Phi(|z|)\}$$

and

$$(\hat{M}_{i1} - \hat{M}_{i2} - z_{0.975} * \sqrt{v(\hat{\tau})}, \hat{M}_{i1} - \hat{M}_{i2} + z_{0.975} * \sqrt{v(\hat{\tau})})$$

where $\Phi(s)$ is the cumulative probability function of the standard normal.

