14.2 Efficacy

Table 14.2.1	Kaplan-Meier Estimates of the Cumulative Percentage of Subjects with Complete Healing	Intent-to-Treat Subjects
Table 14.2.2	Analysis of Change from Baseline in Trans Epidermal Water Loss (TEWL) Measurement	Intent-to-Treat Subjects
Table 14.2.3	Analysis of Change from Baseline in Erythema Measurement	Intent-to-Treat Subjects
Table 14.2.4	Analysis of Change from Baseline in Edema Measurement	Intent-to-Treat Subjects
Table 14.2.5	Analysis of Change from Baseline in the Composite Scar Score Measurement	Intent-to-Treat Subjects
Table 14.2.6	Analysis of Change from Baseline in Painful Score with Arm Resting by Side (Self-Assessment Questions 1)	Intent-to-Treat Subjects
Table 14.2.7	Analysis of Change from Baseline in Painful Score with Arm in Normal Motion (Self-Assessment Questions 3)	Intent-to-Treat Subjects
Table 14.2.8	Analysis of Change from Baseline in Itchy Score (Self-Assessment Questions 5)	Intent-to-Treat Subjects
Table 14.2.9	Summary of Pain with Arm Resting by Side (Self-Assessment Questions 2)	Intent-to-Treat Subjects
Table 14.2.10	Summary of Pain with Arm in Normal Motion (Self-Assessment Questions 4)	Intent-to-Treat Subjects

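### Noon-clock healing times combined with an unspecified censoring time can make the Day 16 step of the primary Kaplan-Meier curve overstate healing

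*SAP*

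**What the plan says.** SAP 4.2.1 defines the primary endpoint as "the time (in days) elapsed from the time of wound creation to 12 PM of the day on which the composite healing score" qualifies; the score qualifies on the day when it "first meets the complete healing criterion of being at least a score of 8". A separate sentence covers sites still below that threshold at the final grading. For these, "the time to complete healing will be censored at the last day on which the composite healing score is available". Protocol 8.3.1 has the same two rules. Neither document gives a clock time for the censoring or says how ties are ordered.

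Protocol 7.1 says that a subject's visits "should be scheduled at approximately the same time of day for each visit (i.e., morning, afternoon, or evening"). This fixes the part of the day within a subject but not across subjects. Under Table 2 and Protocol 7.2.7, every site is graded through Day 16, healed or not.

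SAP 6.3 then applies the estimator: "The survival function (cumulative percentage of wounds healed at each time point) will be estimated by the Kaplan-Meier method for each treatment separately". It derives the medians for the bootstrap test from those same curves. The curve is itself a planned output, as Table 14.2.1 and Figure 14.1.1, both titled "Kaplan-Meier Estimates of the Cumulative Percentage of Subjects with Complete Healing".

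**The concern.** Two sites graded at the same Day 16 visit, one healed and one not, carry the same information about Day 16, so the unhealed site should count in the denominator for every Day 16 healing. The plan does not secure this. Event times shift with the hour of wounding, so Day 16 healings are spread around 16.0. An unhealed site can therefore be removed before a healing that was graded on the same day in another subject. The remaining Day 16 events then act on too small a risk set.

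Without dropout, the share healed by Day 16 is a plain count and the Kaplan-Meier estimate should equal it. Dropping observed unhealed sites early can only push the estimate upward. Arms with almost no unhealed sites are barely touched, while slower arms with some Day 16 healings are flattered. The visible gap between treatments shrinks in a study whose sample size section (Protocol 8.1) says it is meant to estimate effect size. A curve ending at 100% would also contradict the site-level gradings in Listing 16.2.6.1.

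**Working it through.** **Inputs from the documents.** Event clock, threshold of 8, Day 16 limit and censoring sentence: SAP 4.2.1. Visit times that may differ between subjects: Protocol 7.1. Kaplan-Meier per treatment: SAP 6.3. At least 30 completers: Protocol 8.1. The plan states no figure for this point, so there is none to reproduce.

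**Assumed, because the documents do not give them.** Wounding hours, the distribution of healing days and, unless stated, no dropout.

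**Step 1: event times.** A healing on study day *d* in a subject wounded at hour *h* (24-hour clock) has time *d* + (12 − *h*)/24. For Day 16:
- wounded 9 AM: 16 + 3/24 = 16.125
- wounded 3 PM: 16 − 3/24 = 15.875

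**Step 2: two natural readings of the censoring day.**
- (a) Noon of that day on the subject's own clock, the same formula as for events.
- (b) The day number, 16.0.

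**Step 3: worked record.** Take 30 sites. 24 heal by Day 15, 3 heal on Day 16 (wounded 9 AM, 11 AM, 2 PM), and 3 are graded unhealed on Day 16 (wounded 10 AM, 1 PM, 3 PM). The true share healed is 27/30 = 90%. After Day 15, S = 6/30 = 0.200.

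Reading (a), in time order:
- 15.875 censored, 5 left
- 15.917 event: 0.200 × 4/5 = 0.160
- 15.958 censored, 3 left
- 16.042 event: 0.160 × 2/3 = 0.107
- 16.083 censored, 1 left
- 16.125 event: 0.107 × 0/1 = 0, so 100% healed

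Reading (b):
- 15.917 event: 0.200 × 5/6 = 0.167
- 16.0: three censored, 2 left
- 16.042 event: 0.167 × 1/2 = 0.083
- 16.125 event: 0, so 100% healed

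Censoring at 16.5 instead:
- 0.200 × 5/6 × 4/5 × 3/4 = 0.100, so 90% healed, which is correct

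**Step 4: expected size.** Simulation with normal healing day, SD 3, *n* = 30, wounding uniform from 8 AM to 6 PM, no dropout. Entries are percent unhealed at Day 16; the last column is true minus estimate.

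| Mean healing day | True | (a) own noon clock | (b) day number | Excess healed (a) / (b), points |
|---|---|---|---|---|
| 9 | 1.0 | 0.9 | 0.9 | 0.1 / 0.1 |
| 11 | 4.8 | 3.1 | 3.0 | 1.7 / 1.8 |
| 13 | 15.7 | 8.1 | 5.3 | 7.6 / 10.4 |
| 15 | 36.9 | 20.2 | 8.2 | 16.7 / 28.7 |

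Repeat runs move these by a few tenths of a point. With *n* = 40 and 25% dropout the results were nearly the same.

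**Step 5: a different model.** Log-normal healing, log-SD 0.25, wounding 08 to 16 h. At a median of 13 days, 79.8% are truly healed at Day 16, against 88.1% under (a) and 93.8% under (b). The bias was never negative.

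**Step 6: dependence on wounding hours** (same log-normal model, median 13 days).
- All wounding 08 to 12 h: true 79.6%, (a) 88.0%, (b) 98.4%.
- All wounding 12 to 17 h: true 79.7%, (a) 88.2%, (b) 79.7%.

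Reading (a) is biased for any spread of hours. Reading (b) is unbiased only when nobody is wounded before noon.

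**Step 7: what is not affected.** The offsets lie within ±0.5 day, so all events of one day precede all events of the next. Without dropout nothing is censored before the Day 16 group, and the curve after each of Days 1 to 15 equals the raw fraction. In the normal model with means of 9 to 13 days, the Kaplan-Meier median under the own noon clock matched the median under the day + 0.5 rule in every run. At a mean of 16.5 days, the median is truly not reached in 70% of samples but is reported as not reached in only 26% (a) or 17% (b).

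**The case against.** The strongest reply is that the planned inference does not depend on the Day 16 step. SAP 6.1 tests only medians, SAP 6.2 calls all tests exploratory, and both documents say that untreated wounds of this kind usually heal inside 14 days. A reader might infer that the between-product test is compromised. The documents do not support that: medians well before Day 16 do not move. The large entries in the table come from slow arms that the documents do not predict, and at means of 9 to 11 days the error is below one site in 30 (1/30 = 3.3 points). All of this stands. The remaining gap is that the 14-day remark concerns healing in general and does not say when the composite score reaches 8.

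A second reply is that the text gives no censoring clock, so it is not necessarily biased. Reading the last day as the end of that day, or as the day number with all wounding after noon, gives no bias. That also stands, and it rules out saying that the rule must fail. But the end-of-day reading is not written, and Protocol 7.1 allows morning visits.

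Third, the worked record is an unfavourable ordering. Over the 20 possible orders of 3 events and 3 censorings under reading (a), the estimate averages 96.5%. Half of the orders give 100%, and the lowest gives the correct 90%. The record shows what can happen; the simulation shows the expected size.

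**Conclusion.** The point holds for the final step of the primary-endpoint table and figure, under the two natural readings of the censoring sentence. The 2-point and 8-to-10-point figures rest on the assumed 8 AM to 6 PM wounding, SD 3 and *n* = 30, and no such inputs are in the documents. The mechanism and its direction do not rest on them. A median is wrongly reported as reached only if about half or fewer of an arm's sites heal by Day 16.

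Two further inferences are tempting and should not be drawn. One is that the bias rises steadily with the share unhealed. It also needs Day 16 healings and is zero without them. In the log-normal model, reading (a) peaks at about 17 to 18 points for medians of 16 to 18 days and eases to about 15 points at 20 days. The other is that reading the curve at whole-day times would miss healings in subjects wounded before noon. That presupposes a table layout the SAP does not state.

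This is worth correcting before analysis because it concerns a planned primary output and is cheap to remove. It is not a flaw in the hypothesis test over the range of healing times that the documents expect.

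**What to change.** In SAP 4.2.1 and Protocol 8.3.1, choose one time scale and use it for both the curve and the tested medians, since SAP 6.3 derives the medians from the curve. Either of these works:

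- Keep the noon clock for events and replace the censoring sentence with: *a site that has not met the criterion is censored at its last graded study day + 0.5 day, after every possible event time of that day and before any of the next.*
- Use the visit-day number for both events and censorings, with events placed before censorings at ties. This also means rewording the event-time definition.

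Both restored the observed Day 16 share exactly in the no-dropout simulations. Specifying only noon of the last day for censoring would not help, because that is reading (a).

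The cost is essentially one sentence and one programming line, with no new data, visits or subjects. Reported Day 16 healed percentages become slightly less favourable.
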